# C4. Recruitment

# **C4.1** Recruitment strategies

Participants between the ages of 55 to 80 will be recruited using several strategies:-

Strategy	Canada	Australian sites			
		Brisbane	Sydney	Melbourne	Perth
C4.1.1 Network of primary care physicians who see patients with lung cancer	X				
C4.1.2 Social media, newspaper, radio, television	X	X	Х	Х	Х
C4.1.3 Department of Human Services mail out (invitation)				X	

**C4.1.1** In Canada, BCCA is collaborating with a Network of primary care physicians who have historically demonstrated provision of care to lung cancer patients. The Study will invite members of the primary care network to advertise to identify potentially eligible patients and refer them to the Vancouver General Hospital Lung Cancer Screening Centre.

**C4.1.2 Social media, newspapers, radio and television**. As previously used in the Queensland Lung Cancer Screening Study and the Pan-Canadian Early Detection of Lung Cancer Study, this study will utilize existing organizational platforms for advertising the study to the general community through these public accessible media vehicles using electronic social media announcements, public service messages, media releases and targeted advertisement to appropriate parties.

The core information is shown below. Minor modifications will be made to reflect the local situation as needed:

# Could you be at risk of developing lung cancer?

Are you:

- A smoker or recent former smoker?
- Aged between 55 and 80?
- In good general health?

If you answered yes to these questions, you may be eligible to take part in a research study conducted by International Consortium XXXX at XXXX Hospital.

Eligible persons are invited to have a low- dose CT scan to see if this could be a useful way of detecting early lung cancer in healthy people at risk.

If you are interested in participating, please contact the research team at XXX Hospital on (0X) XXX XXXX for more information.

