## 3.0 Study Plan:

- (3.1) Compare the relative sensitivity of the PLCO m2012 ≥1.51% over 6 years lung cancer risk screening threshold versus the USPSTF screening criteria (55-80 years of age who had smoked at least 30 pack-years and former smokers who had stopped smoking for less than 15 years) in newly diagnosed lung cancer patients.
- (3.2) Recruit 8,000 ever smokers between the age of 55 to 80 years from Canada, Australia, Denmark and Italy and prospectively evaluate the sensitivity, specificity and positive predictive value of the PLCOm2012 and USPSTF selection criteria, in two phases:

Phase I – Canada and Australia (4000 participants)

Phase II - Italy and Denmark (4000 participants)

(3.3) Prospectively evaluate the PanCan lung nodule malignancy risk prediction tool and Lung-RADS for management of lung nodules detected by screening LDCT.

**Significance:** This project addresses the important issues of identifying optimal risk selection criteria for LDCT lung cancer screening in the general population as well as the accuracy of the PanCan Lung Nodule Malignancy Risk prediction tool for management of LDCT detected lung nodules.

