**Figure 7. Lung Nodule Management Protocol** 

## C2. Participant Inclusion and Exclusion Criteria

## C2.1 Inclusion Criteria

- Women or men age 55 to 80 years.
- Current or former smokers. A former smoker is defined as one who has stopped smoking for one or more years.
- An estimated 6-year lung cancer risk of ≥1.51% based on the PLCOm2012 risk prediction model
  or ≥ 30 pack-years smoking history (pack-year is defined as number of pack of cigarettes smoked per
  day multiply by the number of years smoked. If a participant stopped smoking for 6 months or more
  and then restarted smoking again, the time will be subtracted from the total duration of smoking in
  0.5-year increments)
- ECOG performance status 0 or 1.
- Capable of providing, informed consent for screening procedures (low dose spiral CT)

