## C4.2 Eligibility assessment process (Figure 2)

C4.2.1 People interested in participating in the study will telephone the study centre (free call number) and speak with the research coordinator/assistant or will leave contact details for return calls. People approached through direct mail out will also be given a telephone number to call or will be provided with a written form (including contact details) and reply-paid envelope to return to the study centre. The research coordinator at each study centre will conduct an initial telephone eligibility assessment using an innovative web-based lung cancer risk assessment tool (PLCOm2012 developed by [name]

[name]). This tool is available as an iPhone app or iPad app or accessed online. This tool can automatically display the lung cancer risk and indicate whether a person is eligible for LDCT screening according to the PLCOm2012-risk≥0.0151 selection criteria or the USPSTF criteria (Figure 2).

- C4.2.2 Those who meet the PLCOm2012 1.51%/6 years lung cancer risk criteria or the USPSTF screening criteria (current smokers who have smoked at least 30 pack-years and former smokers who have smoked 30 pack-years and who have stopped smoking for less than 15 years) will be asked a further series of questions to assess eligibility based on all inclusion/exclusion criteria. Those who are eligible will be invited for a face-to-face meeting to verify smoking history and smoking status (for former smokers by urinary cotinine or exhaled carbon monoxide), inclusion/exclusion criteria, explanation of the risks and benefits of LDCT screening. Participants who are unable to travel twice will have their smoking status verified on the day of the CT scan. Informed consent will be obtained for the main study and for optional studies (e.g., outdoor and household air pollution exposure and blood specimen collection) before the CT scan.
- C4.2.3 A study number will be assigned. Those not eligible for screening will be assigned a study number with additional code to denote ineligibility.
- C4.2.4 Informed consent will be obtained using the attached study patient information and consent forms (Appendix XXX)
- C4.2.4.1 Eligible participants who have provided informed consent will be invited to undergo CT screening and will be invited to consent to be involved in sub-studies.

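### The core advertisement asks for recent former smokers only, which is narrower than eligibility and may under-recruit long-term quitters, who can never be USPSTF-positive

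*Protocol*

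**What the plan says.** C4.1.2 of the protocol introduces the media advertisement with "The core information is shown below. Minor modifications will be made to reflect the local situation as needed". Its first question to the reader is "A smoker or recent former smoker", and *recent* is not defined there or elsewhere.

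The population is described more widely in other sections:

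- Study plan 3.2: "Recruit 8,000 ever smokers between the age of 55 to 80 years".
- C2.1: "Current or former smokers. A former smoker is defined as one who has stopped smoking for one or more years". This sets a minimum time since stopping and no maximum.
- C4.2.2 admits "Those who meet the PLCOm2012 1.51%/6 years lung cancer risk criteria or the USPSTF screening criteria". Under the USPSTF rule, former smokers are those "who have stopped smoking for less than 15 years".
- C2.1 gives the alternative to the PLCOm2012 threshold as "≥ 30 pack-years smoking history", with no quit-time limit.

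The C4.1 strategy table lists media at all five sites. It is the only listed channel at Brisbane, Sydney and Perth. Vancouver also has a primary care network (C4.1.1) and Melbourne a random mail-out by age and postcode (C4.1.3).

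**The concern.** One of the two rules under comparison has a quit-time cut-off. A person who stopped 15 or more years ago cannot be USPSTF-positive, whatever their pack-years. In the paired comparison that person is either PLCOm2012-only or negative on both rules. An advertisement that discourages people who stopped long ago therefore does not act evenly on the two rules.

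Two results are exposed. The sensitivity comparison in Aim 1 depends on the discordant cancers, and the PLCOm2012-only cancers are the larger share of them. The long-term follow-up group in C4.2.2.2 feeds the C11 outcome on people who meet neither rule but develop lung cancer, and deterred quitters who are negative on both rules would be missing from it. The telephone assessment in C4.2 uses the full tool, but it reaches only those who respond. Under-recruitment of this kind cannot be repaired after accrual closes.

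**Working it through.** **Inputs (C13.1).** N = 4000; 155 cancers; proportion positive 85.3% (USPSTF) and 77.8% (PLCOm2012); sensitivity 83.8% and 94.3%; correlation between the criteria -0.222.

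**Reproducing the plan's figures.** Suppose everyone in the sample is positive on at least one rule:

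- both = 0.853 + 0.778 - 1 = 63.1%
- USPSTF-only = 1 - 0.778 = 22.2%
- PLCOm2012-only = 1 - 0.853 = 14.7%
- correlation = -(0.222 × 0.147)/√(0.853 × 0.147 × 0.778 × 0.222) = -0.2218

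This matches the stated -0.222, so these are the cells behind C13.1. At N = 4000 they are 2524, 888 and 588 people.

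The stated power above 90% reproduces for the proportion selected (above 99.9%). For sensitivity, the McNemar calculation on these cells with 155 cancers gives 80%. That is a separate matter, so the results below are in percentage points, not power.

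**Cancers by cell**, assuming every cancer is positive on at least one rule:

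- both = 155 × (0.838 + 0.943 - 1) = 155 × 0.781 = 121.1
- PLCOm2012-only = 155 × (1 - 0.838) = 25.1
- USPSTF-only = 155 × (1 - 0.943) = 8.8
- difference = (25.1 - 8.8)/155 = 10.5 points, as stated

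The advantage rests on about 25 against 9 discordant cancers.

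**Illustrative loss.** Remove a fraction f of the PLCOm2012-only cell and g of the USPSTF-only cell, with the same cancer rate in those lost as in those who stay:

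- sensitivity difference = [25.11(1 - f) - 8.835(1 - g)] / [121.055 + 25.11(1 - f) + 8.835(1 - g)]
- selection ratio, PLCOm2012 to USPSTF = [2524 + 588(1 - f)] / [2524 + 888(1 - g)]

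Both f and g are assumptions; the protocol gives no figure for either.

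| f | g | Sensitivity difference | Selection ratio |
|---|---|---|---|
| 0 | 0 | 16.28/155.00 = 10.5 points | 3112/3412 = 0.91 |
| 10% | 0 | 13.76/152.49 = 9.0 points | 3053/3412 = 0.89 |
| 25% | 0 | 10.00/148.72 = 6.7 points | 2965/3412 = 0.87 |
| 25% | 25% | 12.21/146.51 = 8.3 points | 2965/3190 = 0.93 |

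In each scenario the sensitivity advantage shrinks. The selection ratio falls when only PLCOm2012-only people are lost and rises when both discordant cells lose equally. Loss from the both-positive cell is not modelled.

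**The case against.** The strongest reply is that this is recruitment copy and not an eligibility rule. It says only that a reader may be eligible, and every caller is assessed with the full tool. That is true, but assessment does not recover people who never call.

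Several further points stand and limit the finding:

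- **Who is in the cell.** PLCOm2012-only people also include current smokers and recent quitters with under 30 pack-years, whom the wording does not deter. The protocol does not give the share who stopped 15 or more years ago. The real f is that share, times the share reached only by this text, times the share put off by it; none is known.
- **USPSTF-positive people may be deterred too.** Someone who stopped 10 to 14 years ago can meet USPSTF and still not feel *recent*. One cannot assume that the word costs that rule nothing.
- **Other sources.** The Vancouver network and the Melbourne mail-out are described without a recency limit. Vancouver supplies 2,000 of the 4,000 Phase I participants. The comparison in an estimated 1,400 newly diagnosed patients (3.1, C5.0) does not depend on the advertisement.
- **Data already collected.** The Figure 2 questionnaire records the age at which former smokers stopped.

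A reader might infer that the wording empties the PLCOm2012-only cell and so biases both halves of hypothesis 1 in a known direction. The documents do not support that. The cell is mixed, the loss is unquantified, and the direction for the proportion selected reverses under an equally admissible assumption.

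**Conclusion.** The advertisement is narrower than the population the protocol sets out to recruit, and the mismatch falls on a characteristic that one of the two rules uses as a cut-off. It may under-recruit part of the PLCOm2012-only cell and of the both-negative follow-up group, and it can understate PLCOm2012's sensitivity advantage. This is an avoidable selection risk of unknown size, not a demonstrated bias. The 6.7 to 9.0 points in the table are illustrations: they rest on assumed losses, on equal cancer rates in those lost and kept, and on every cancer being positive on at least one rule. The effect on the proportion selected is undetermined. The risk is greatest at the three sites with no other listed channel.

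The statement that a quitter of 15 or more years can be scanned only through PLCOm2012 holds under C4.2.2 but not under C2.1, whose pack-year route has no quit limit. The asymmetry survives either reading, because such a person remains USPSTF-negative. The two sections nevertheless contradict each other.

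**What to change.** - Change the advertisement line to: *A current or former smoker (no matter how long ago you stopped)?*
- State in C4.1.2 that local modifications may not add a recency condition.
- Show the distribution of years since quitting by recruitment route, so that any remaining effect is visible. Age at stopping is already collected; the recruitment route must be recorded with it.
- Separately, reconcile the pack-year route in C2.1 with the USPSTF wording in C4.2.2.

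The cost is one phrase, an ethics notification, and more calls from people who prove ineligible. Those callers are not wasted, since C4.2.2.2 asks them to join long-term follow-up.

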# C4.1.3 Department of Human Services mail out (Melbourne).

Once ethics approval has been obtained, we will apply to Department of Human Services (DHS) to conduct a mail out to people aged 55 to 80 living in areas close to the study centre. The mail out will be conducted by DHS on behalf of the organisation conducting the study. Participants who are aged 55 to 80 living in pre-selected regions based on post codes will be randomly selected from the DHS Medicare database. DHS will conduct the mail out on our behalf so that identifiable data is not provided to us directly. The mail out will include study information and an invitation to take part along with telephone contact details and a reply-paid envelope.

## C4.2 Eligibility assessment process (Figure 2)

C4.2.1 People interested in participating in the study will telephone the study centre (free call number) and speak with the research coordinator/assistant or will leave contact details for return calls. People approached through direct mail out will also be given a telephone number to call or will be provided with a written form (including contact details) and reply-paid envelope to return to the study centre. The research coordinator at each study centre will conduct an initial telephone eligibility assessment using an innovative web-based lung cancer risk assessment tool (PLCOm2012 developed by [name]

[name]). This tool is available as an iPhone app or iPad app or accessed online. This tool can automatically display the lung cancer risk and indicate whether a person is eligible for LDCT screening according to the PLCOm2012-risk≥0.0151 selection criteria or the USPSTF criteria (Figure 2).

- C4.2.2 Those who meet the PLCOm2012 1.51%/6 years lung cancer risk criteria or the USPSTF screening criteria (current smokers who have smoked at least 30 pack-years and former smokers who have smoked 30 pack-years and who have stopped smoking for less than 15 years) will be asked a further series of questions to assess eligibility based on all inclusion/exclusion criteria. Those who are eligible will be invited for a face-to-face meeting to verify smoking history and smoking status (for former smokers by urinary cotinine or exhaled carbon monoxide), inclusion/exclusion criteria, explanation of the risks and benefits of LDCT screening. Participants who are unable to travel twice will have their smoking status verified on the day of the CT scan. Informed consent will be obtained for the main study and for optional studies (e.g., outdoor and household air pollution exposure and blood specimen collection) before the CT scan.
- C4.2.3 A study number will be assigned. Those not eligible for screening will be assigned a study number with additional code to denote ineligibility.
- C4.2.4 Informed consent will be obtained using the attached study patient information and consent forms (Appendix XXX)
- C4.2.4.1 Eligible participants who have provided informed consent will be invited to undergo CT screening and will be invited to consent to be involved in sub-studies.
- C4.2.2.2 Non eligible people who expressed an interest to be screened but do not meet either screening inclusion criteria or are excluded for other reasons will be asked to take part in long term follow up.
- C4.2.2.3 In addition, those who are eligible for screening but decline to take part after a discussion about the risks and benefits will be offered participation in long term follow up.

We will seek consent for long term linkages studies on these groups (C4.2.2.2 and C4.2.2.3) of participants using an opt-out process.

In Australia, consent will be sought to link participant data with state-based cancer registries and the National Death Index and MBS records in order to determine the incidence of lung cancer in those who do not fulfill the screening inclusion criteria and also to assess whether those who are not eligible subsequently undergo CT scanning outside of the study.

In Canada, consent will be sought to link participant data with the Cancer Registry.

Participants will be offered the opportunity to opt out at any time including at the time of the telephone interview, those who do not opt out at this point will be sent a participant information sheet and opt out form and asked to return to the study centre by pre-paid envelopes if **they do not** wish to take part in the linkages study. They will be asked to return the form within 3 weeks and if a form has not been received within that time frame it will be assumed that they do not object to participation in the linkages study.

Consent may also be sought for participation in Optional Sub-studies such as air pollution surveys, biomarkers and quality of life.

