## C2.2 Exclusion Criteria

- Clinical symptoms suspicious for lung cancer e.g., hemoptysis, chest pain, weight loss
- Any medical condition, such as severe heart disease (e.g. unstable angina, chronic congestive heart failure), acute or chronic respiratory failure, home oxygen therapy, bleeding disorder, that in the opinion of the investigator could jeopardize the subject's safety during participation in the study or unlikely to benefit from screening due to shortened life-expectancy from the co-morbidities
- Have been previously diagnosed with lung cancer
- Have had other non-curatively treated cancer outside the lung.
- Pregnancy
- Pneumonia or bronchitis requiring antibiotic treatment within the last 12 weeks
- Unwilling to have a spiral chest CT
- Chest CT within 2 years
- Does not fit into CT scanner table due to gross obesity
- Cannot lie on CT scanning table on the back with arms over the head
- Received chemotherapy or cytotoxic drugs within the last 6 months
- Unwilling to sign a consent

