#### C11. Outcome Evaluation

The outcomes of interest in this study are:

- the number needs to be screened to detect one cancer with the PLCOm2012 versus the USPSTF selection criteria
- proportion of participants who do not meet either the PLCOm2012 or USPSTF screening selection criteria but develop lung cancer
- cancer detection rate
- the number of interval lung cancer cases
- recall rate
- Invasive procedure rate
- Non-malignant biopsy/surgery rate
- adverse events (morbidity related to bronchoscopy, biopsies, surgery or other treatments)
- resection rate
- stage distribution of the lung cancers
- Mortality (lung cancer, all causes)
- smoking cessation rate (for current smokers)
- rate of detection of other incidental significant treatable diseases
- type and costs of downstream investigation and treatment related to abnormalities found by the screening procedures whether the final diagnosis is lung cancer or not

identify logistics/barriers for an early detection program

The participants will be followed regularly at annual intervals for four years either by telephone or personal visits, and details of all outpatient visits and use of allied health services related to lung cancer diagnosis or treatment will be obtained. Additional information regarding development of lung cancer or death from lung cancer beyond 4 years will be obtained from Cancer Registries and Death Registries. Change in smoking status will be monitored annually using urinary cotinine/exhaled carbon monoxide.

Diagnostic procedures related to the early detection procedures will be tracked by the site study coordinator. The lung cancer cases will be evaluated by the Steering Committee. The histology cell type, TNM stage, treatment procedures, length of hospital stay, type of hospital ward (Intensive Care, stepdown unit, general ward), physician visits etc. will be tracked by the site study coordinator and submitted to the CC database. For lung cancer cases (both prevalent and interval) that are not managed by the site investigators, the site coordinator will obtain the procedure and pathology reports as well as the tissue blocks from the outside facility for review.

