Screening Questionnaire Today's Date: Initials: Birth date: Postal Code: ddmmyy Gender: Male Current Age: ∃ Female Race/Ethnicity: Aboriginal (e.g. First Nations, Métis, Inuit)  $\square$ Latin American/Hispanic Ш South Asian (e.g. India, Sri Lanka, Ш Ш Pakistan, Bangladesh) Southeast Asian (e.g. Malaysia, Indonesia, Viet Black (African or Caribbean descent) Ш East Asian (e.g. China, Japan, Korea, Taiwan) Ш West Asian (e.g. Turkey, Iran, Afghanistan) Ш Filipino 1 1 Ш White (European/Middle Eastern/North African) Other ethnic group not listed above Jewish Ш 1) How old were you when you started smoking regularly? years old 2) Are you still smoking now? Yes No 🖂 3) a. Still Smoking Now Yes: if you are still smoking now, were there periods longer than a year when you did not smoke? Yes No No For how many years did you not smoke between starting smoking and now? \_\_yrs b. Still Smoking Now No: Between the time you started smoking and finally quit smoking, were there periods longer than a year when you did not smoke? Yes \( \sigma \) No \( \sigma \) . For how many years did you not smoke between starting smoking and permanently quitting smoking? \_yrs 4) If you are not currently smoking, how old were you when you stopped? years old On average, when you smoke(d), how many cigarettes a day do (did) you smoke? \_\_\_\_ 6) Have you ever been diagnosed with any cancer(s)? Do not include cancers of the skin other than melanoma. Were any of your blood relatives, mother, father, siblings, children, including half-sisters and half-brothers ever diagnosed with lung cancer? Yes 7) What is the highest level of education you have completed? Some college/University University Graduate 8th grade or less 9th grade to 11th grade High school graduate Post graduate/Professional Degree Technical/Vocational School certificate 8) Have you had a chest x-ray within the last three years? (circle one): Yes No No How many: 9) Has a doctor ever told you that you have Chronic Obstructive Pulmonary Disease (COPD), Emphysema or Chronic Bronchitis? Yes 📋 No 🗌 10) Have you had a CT scan of your chest within the last two years? Yes ☐ No ☐ \_\_\_\_ lbs/\_\_\_Kg 11) Current Height: \_\_ in/\_\_\_\_ cm 12) Current Weight: Estimated Lung Cancer Risk Index PLCO PanCan USPSTF

Figure 3. Lung-RADs Classification (http://www.acr.org/Quality-Safety/Resources/LungRAD)

Lung-RADS for nodules at baseline	Findings	Management		

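### Callers negative on both selection rules are never asked about suspicious symptoms, so the proportion of them who develop lung cancer can be inflated by cancers already symptomatic at the call

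*Protocol*

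**What the plan says.** The order of assessment is set in Protocol C4.2.

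- **First step, all callers (C4.2.1).** The coordinator "will conduct an initial telephone eligibility assessment using an innovative web-based lung cancer risk assessment tool". The form behind it (Figure 2) records age, smoking history and cancer history: "Have you ever been diagnosed with any cancer(s)? Do not include cancers of the skin other than melanoma". Its readable text has no question on symptoms.
- **Second step, rule-positive callers only (C4.2.2).** Those who meet PLCOm2012 or USPSTF "will be asked a further series of questions to assess eligibility based on all inclusion/exclusion criteria". The exclusions in C2.2 include "Clinical symptoms suspicious for lung cancer e.g., hemoptysis, chest pain, weight loss" and "Have been previously diagnosed with lung cancer".
- **Follow-up of the others (C4.2.2.2).** Interested people who "do not meet either screening inclusion criteria or are excluded for other reasons will be asked to take part in long term follow up". This is opt-out registry linkage. In Australia it is sought, among other reasons, "in order to determine the incidence of lung cancer in those who do not fulfill the screening inclusion criteria". No clinical exclusion is stated for this group.
- **Outcome (C11).** One listed outcome is the "proportion of participants who do not meet either the PLCOm2012 or USPSTF screening selection criteria but develop lung cancer".

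**The concern.** The C11 outcome is how the trial learns what both rules leave out, which bears on Objective 1.1 (optimal selection criteria). Study Plan 3.2 also promises prospective sensitivity and specificity for each rule, and the linkage group is the main source of people negative on both.

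Someone who rings because of a worrying symptom, scores negative on both rules and is diagnosed soon afterwards counts as a cancer that risk selection missed. A rule-positive caller with the same symptom is kept out of the screened cohort. If screened rule-positive people are set against all rule-negative people, the two groups have passed different entry filters.

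The gap lies in data collection. A symptom question that was never asked cannot be supplied later by an analysis plan.

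**Working it through.** **1. Passages side by side.**

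| Item | Rule-positive callers | Rule-negative callers |
|---|---|---|
| Age, smoking | asked (Figure 2) | asked (Figure 2) |
| Any previous cancer | asked (Figure 2) | asked (Figure 2) |
| Previous lung cancer as an exclusion | applied (C2.2, C4.2.2) | not stated |
| Suspicious symptoms | asked and applied (C2.2, C4.2.2) | not asked |
| Cancer detection | LDCT if screened, plus follow-up | registry linkage, no study LDCT |

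Only symptom status is entirely absent for rule-negative callers.

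**2. Is there a stated figure to reproduce?** None for this outcome: the protocol gives no size, expected rate or target for the rule-negative group. The nearest is C13.1: 4000 x 0.039 = 156 lung cancers, against 155 stated, which agrees to rounding.

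**3. Possible inflation (all inputs assumed).** Let r0 be the six-year risk in rule-negative people free of both exclusions, f the share who would fail an exclusion question, and q their probability of a recorded lung cancer.

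Observed = (1 - f) x r0 + f x q, so observed / r0 = 1 + f x (q/r0 - 1).

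Ranges: r0 0.3% to 0.8% (below the 1.51% threshold), f 0.2% to 2%, q 2% to 10%.

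| Case | r0 | f | q | Observed | Ratio |
|---|---|---|---|---|---|
| Low | 0.8% | 0.2% | 2% | 0.802% | 1.00 |
| Mid | 0.5% | 1% | 5% | 0.545% | 1.09 |
| High | 0.3% | 2% | 10% | 0.494% | 1.65 |

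**4. Absolute sensitivity.** Take C13.1: 155 cancers, sensitivities 83.8% (USPSTF) and 94.3% (PLCOm2012). Add k hypothetical cancers negative on both rules. Each sensitivity becomes 155 x sensitivity / (155 + k).

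| k | USPSTF | PLCOm2012 | Difference | Ratio |
|---|---|---|---|---|
| 0 | 83.8% | 94.3% | 10.5 points | 1.125 |
| 10 | 129.89/165 = 78.7% | 146.165/165 = 88.6% | 9.9 points | 1.125 |
| 20 | 129.89/175 = 74.2% | 146.165/175 = 83.5% | 9.3 points | 1.125 |

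Both absolute values fall and the difference narrows a little. The ratio stays the same.

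**5. Paired test.** McNemar's test uses only cancers on which the rules disagree. Cancers negative on both add nothing to either discordant cell. The power sample in C13.1 also appears to contain no such people. With 85.3% and 77.8% positive, the lowest possible correlation is (0.853 + 0.778 - 1 - 0.853 x 0.778) / sqrt(0.853 x 0.147 x 0.778 x 0.222) = -0.222. That is the stated value, and it is reached only when nobody is negative on both.

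**The case against.** The case on the other side is substantial, and it rules out four stronger readings that a reader might infer.

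- **That the outcome is inflated.** Only that it can be. Rule-negative people have no study LDCT, so their cancers surface through linkage, which lowers their count relative to a CT-screened cohort. The advertisement also asks for people in good general health, although that is self-selection and not an exclusion. The net direction is unknown.
- **That previous lung cancers pass unseen into the count.** Figure 2 asks every caller about previous cancer, registries carry diagnosis dates, and C11 and C4.2 speak of developing cancer and of incidence, which imply new cases. At most, a stated rule for using these data is missing, and that could sit in an analysis plan.
- **That never-smokers and people outside 55-80 are counted.** The Melbourne mail-out has no smoking filter and C4.2.2.2 sets no limit. But Study Plan 3.2 concerns ever-smokers aged 55-80, and Figure 2 records age and smoking. The denominator can be restricted from data already collected.
- **That the comparison of the two rules is biased.** The paired test and the sensitivity ratio do not change.

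Two further points stand. Rule-positive people with exclusions are also offered follow-up, so the asymmetry arises only when screened rule-positive people are set against unfiltered rule-negative people. And this is one of many C11 outcomes, with no target or power attached.

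None of this supplies the missing symptom question. Two opposing biases of unknown size do not make the outcome sound.

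**Conclusion.** The point holds in limited form. As C4.2 is written, rule-negative callers enter linkage with symptom status unknown, while the screened cohort is cleared of suspicious symptoms and previous lung cancer. The C11 proportion can be inflated by cancers already symptomatic at the call, and any absolute sensitivity using this group can be correspondingly lowered.

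The size cannot be derived from the protocol. The range of 1.00 to 1.65, mid-case 1.09, rests wholly on the assumed r0, f and q and takes no account of the opposite effect of finding cancers without LDCT. The k values are illustrative.

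The conclusion also rests on the readable text of Figure 2 and on the wording of C4.2. Figure 6, the recruitment flow diagram, was not readable in the copy at hand. If it shows a symptom question before the rule result, C4.2 should be brought into line with it.

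The change is worth making because it is cheap now and symptom status cannot be fully recovered later.

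**What to change.** 1. In C4.2.1, ask every caller the C2.2 items on suspicious symptoms and previous lung cancer at the initial telephone assessment, before the rule result decides the pathway, and record the answers.
2. In C11, report the outcome in ever-smokers aged 55-80 who are negative on both rules and free of both at entry, alongside the unrestricted figure. Age and smoking are already in Figure 2.
3. Optionally, add an analysis omitting cancers registered soon after the call. Treat it as a sensitivity check only: it also removes prevalent cancers from rule-negative people, whereas baseline LDCT counts such cancers among rule-positive people, so on its own it could understate what the rules miss.

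Cost: a slightly longer call for people who will not be screened, and a somewhat smaller denominator for the restricted figure.
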